5.1.4 Study Day – Visit 2 (Week 12 ± 7 days)

The research coordinator will call the subject 1-2 days before the visit as a reminder. The coordinator will instruct the subject that they may maintain their typical enteral intake but to avoid heavy exercise for 12 hours before the study day assessment. Subjects will be instructed to take their routine medications on the morning of the visit and to bring their medications and a snack or meal with them to the visit to take at the center as needed.

The subject will arrive at the study site outpatient clinic or clinical research center. The following procedures will be performed:

- Electrocardiogram
- Echocardiography
- Interim medical history
- Review current medications
- WHO functional class assessment
- Vital signs
- Physical exam
- Review of inclusion/exclusion criteria
- Complete SF-36 and emPHasis-10 forms
- Six minute walk test
- Review study drug compliance
- Review diary and instructions
- Dispense supply of study drug
- Reinforce instructions on recording of new medications and dose changes
- Reinforce instructions on bringing the subject's routine and study medications to all visits

- Reinforce counseling regarding birth control

Echocardiography will be performed. The investigator or research nurse will take a history/interim history and perform a physical examination (examination by physician) including checking vital signs, and review current medications. The subject will complete the SF36 and emPHasis-10. The subject will then perform a six minute walk test (6MWT).

Once all procedures are complete and study drug provided, the research coordinator will thank the subject for his/her attendance and reinforce compliance with the study medication and protocol. The subject's primary PAH physician and medical doctor will be alerted to the subject's continuing participation in the clinical trial.

5.1.5 Phone Call (Week 15 ± 2 days; Week 18 ± 2 days; Week 21 ± 2 days)

The research coordinator will call the subject. Symptoms and potential side effects will be assessed and changes in medications will be reviewed/recorded. Pregnancy avoidance will be stressed. Medication compliance will be assessed and reinforced.

5.1.6 Study Day – Visit 3 (Week 24 ± 3 days)

The research coordinator will call the subject 1-2 days before the visit as a reminder. The coordinator will instruct the subject to not eat or drink (except water) and to avoid heavy exercise for 12 hours before the study day assessment. Subjects will be instructed to take their routine medications on the morning of the visit and to bring their medications and a snack or meal with them to the visit to take at the center after blood draw.

The subject will arrive at the study site outpatient clinic or clinical research center. The following procedures will be performed:

- Phlebotomy
- Urine collection
- Electrocardiogram
- Echocardiography
- Eat a small snack
- Interim medical history
- Review current medications
- WHO functional class assessment
- Vital signs
- Physical exam
- ESR-specific PET study
- Complete SF-36 and emPHasis-10 forms
- Six minute walk test
- Review study drug compliance
- Turn in study diary and any remaining study medication

Fasting urine sample and blood samples for study assays will be processed and banked. Echocardiography will be performed. After the echocardiogram, the subject will have the opportunity to eat a snack. The investigator or research nurse will take a history/interim history and perform a physical examination including checking vital signs, and review current medications. ESR-specific PET study will be conducted. The subject will complete the SF36 and emPHasis-10. The subject will then perform a six minute walk test (6MWT).

Once all procedures are complete the research coordinator will thank the subject for his/her attendance and study participation. The subject's primary PAH physician and medical doctor will be alerted to the subject's completed participation in the clinical trial.

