3.2.2 Exclusion criteria

- Current treatment with estrogen, progesterone, or any form of sex hormone therapy.
- Current treatment with anti-sex hormone therapy (e.g., anastrozole, fulvestrant, tamoxifen, leuprolide acetate (lupron) or other centrally-acting hormone agents).
- WHO Functional Class IV status.
- History of, or current, breast, uterine, ovarian, or testicular cancer.
- Current pregnancy, or prior pregnancy within 3 months of enrollment.
- Initiation of PAH therapy (prostacyclin analogues, endothelin-1 receptor antagonists, phosphodiesterase-5 inhibitors, riociguat, selexipag) within three months of enrollment; the dose must be stable for at least three months prior to Baseline Visit. Of note, PAH therapy, including diuretics, which is stopped and then restarted or has dose changes which are not related to initiation and up titration will be allowed within 3 months prior to the Baseline Visit, and during the trial for subjects.

- History of thromboembolic event.
- Hospitalized or acutely ill.
- Hypercalcemia.
- Enrollment in a clinical trial or concurrent use of another investigational drug (non FDA approved) or device therapy within 30 days of screening visit.
- Enrollment in any pharmacologic clinical trial within one month of screening.
- Due to potential drug interactions with tamoxifen, subjects using bosentan (CYP3A4) or selexipag (CYP2C8) will be excluded.
- Due to the concerns of pregnancy during PAH and with tamoxifen use, pre-menopausal female subjects will be excluded who do not use at least two forms of contraception (e.g., non-hormonal IUD plus the use of a barrier contraceptive method).

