5.1.2 Study Day – Visit 1 (Baseline)

Informed consent will occur at the time of the baseline visit.

The research coordinator will call the subject 1-2 days before the visit as a reminder. The coordinator will instruct the subject to not eat or drink (except water) and to avoid heavy exercise for 12 hours before the study day assessment. Subjects will be instructed to take their routine medications on the morning of the visit and to bring their

medications and a snack or meal with them to the visit to take at the center after blood draw.

Baseline information will be used to characterize the participants and to compare the experimental groups with regards to demographics and other variables. Eligibility criteria will be confirmed prior to randomization to treatment group.

The subject will arrive at the study site outpatient clinic or clinical research center. The following procedures will be performed:

- Phlebotomy
- Urine collection
- Electrocardiogram
- Echocardiography
- Eat a small snack
- Interim medical history
- Review current medications
- WHO functional class assessment
- Vital signs
- Physical exam
- Review of inclusion/exclusion criteria
- ESR-specific PET study
- Complete SF-36 and emPHasis-10 forms
- Six minute walk test
- Randomization to treatment group
- Provide diary and instructions
- Dispense supply of study drug
- Reinforce instructions on recording of new medications and dose changes
- Reinforce instructions on bringing the subject's routine and study medications to all visits
- Reinforce counseling regarding birth control with premenopausal female subjects

Fasting serumpregnancy test will be performed. Fasting urine sample and fasting blood samples for study assays will be processed and banked. Echocardiography will be performed. After the electrocardiogram and echocardiogram, the subject will have the opportunity to eat a snack. The investigator or research nurse will take a history/interim history, check vital signs, and review current medications. A physician will perform a physical examination and review current medications. ESR-specific PET study will be conducted. The subject will complete the SF36 and emPHasis-10. The subject will then perform a six minute walk test (6MWT).

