5.2 Schedule of Study Procedures and Assessments

The table below summarizes the study assessments and procedures.

Table 1. Study Assessments and Procedures

Procedure		Baseline	Wk 1	Wk 3	Wk 6	Wk 9	Wk 12	Wk 15	Wk 18	Wk 21	Wk 24	Wk 25
Call #		1	2	3	4			5	6	7		8
Visit #		1					2				3	
Informed Consent												
Clinical Assessments												
Medical Hx		x										
Symptoms assessment			x	x	x	x	x	x	x	x	x	x
Medications		x	x	x	x	x	x	x	x	x	x	
Vital Signs		x					x				x	
Physical Exam		x					x				x	
WHO Functional Class		x					x				x	
Testing												
Urine collection		x									x	
Phlebotomy		x									x	
6MWTD		x					x				x	
ECG		x					x				x	
SF-36 and emphasis-10		x					x				x	
Imaging												
Echocardiogram		x					x				x	
ESR-specific PET study		x									x	
Study Procedures												
Dispense study drug or placebo		x					x					
Review adverse events			x	x	x	x	x	x	x	x	x	x
Review study drug/placebo diary & compliance			x	x	x	x	x	x	x	x	x	

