9.3 Laboratory values

The following clinical laboratory tests will be measured at baseline.

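### The visit text names a pregnancy test only at baseline, with none before the Week 12 re-dispensing or the Week 24 FES-PET tracer, although pre-menopausal women are enrolled

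*Combined protocol and SAP*

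**What the plan says.** The Abstract admits pre- and post-menopausal women as well as men. Section 3.2.2 excludes "Current pregnancy, or prior pregnancy within 3 months of enrollment" and also excludes pre-menopausal women who are not using two contraceptive methods.

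- **Baseline (5.1.2):** "Fasting serumpregnancy test will be performed. Fasting urine sample and fasting blood samples for study assays will be processed and banked". The first FES-PET scan and the first drug supply belong to this visit.
- **Laboratory list (9.3):** "The following clinical laboratory tests will be measured at baseline". Serum hCG is the entry at 9.3.7.
- **Week 12 (5.1.4):** the procedures include "Review of inclusion/exclusion criteria", "Dispense supply of study drug" and birth-control counselling. Neither blood nor urine sampling is listed.
- **Week 24 (5.1.6):** "Fasting urine sample and blood samples for study assays will be processed and banked" and, further on in the same paragraph, "checking vital signs, and review current medications. ESR-specific PET study will be conducted". An interim history and physical examination are listed. A criteria review and birth-control counselling are not.
- **Telephone calls (5.1.3, 5.1.5):** avoiding pregnancy is raised at seven on-treatment calls (Weeks 1, 3, 6, 9, 15, 18 and 21).
- **Table 1 (5.2):** phlebotomy and urine collection are marked at baseline and Week 24 only. There is no pregnancy-test row.

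Section 9.6 confirms that the PET tracer is radioactive.

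**The concern.** The protocol tests for pregnancy at the visit where drug and tracer are first given, but names no test when either is given again. A woman who conceived after baseline and did not yet know it could pass a history, a criteria review and a counselling conversation. She could then receive a further supply of blinded study drug at Week 12 or a second tracer dose at Week 24.

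The protocol itself treats pregnancy as a serious matter in this population. It makes current pregnancy an exclusion. It justifies two-method contraception by concerns about pregnancy both in PAH and on tamoxifen. What is at stake is participant safety; no estimate or test of the treatment effect is involved.

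**Working it through.** No plan figure needs reproducing. The check sets the visits side by side and counts days from the visit windows.

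**Exposure against named checks (5.1.2, 5.1.4, 5.1.6, Table 1)**

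| Visit | Exposure | Blood or urine listed | Pregnancy test named | Other checks at the visit |
|---|---|---|---|---|
| Baseline | First tracer, first dispensing | Both | Yes, serum | Criteria review, counselling |
| Week 12 | Second dispensing | Neither | No | Criteria review, counselling |
| Week 24 | Second tracer | Both | No | History, examination |

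The baseline and Week 24 narratives use nearly the same sampling sentence. At baseline a pregnancy-test sentence precedes it; at Week 24 nothing does.

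**Time since the only named test.** Days are counted from the baseline visit, taken as the day of the test.

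- Week 12: 12 × 7 = 84, ± 7, so days 77 to 91.
- Week 24: 24 × 7 = 168, ± 3, so days 165 to 171.
- If weeks run instead from the first dose, one day after baseline, each figure rises by 1 (78 to 92 and 166 to 172).

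**Time from the last softer check to the Week 24 tracer**

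- Week 12 criteria review: 165 − 91 = 74 to 171 − 77 = 94 days.
- Week 21 call: 21 × 7 = 147, ± 2, so days 145 to 149. The gap is 165 − 149 = 16 to 171 − 145 = 26 days.

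**Coverage**

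- Dispensings: a named test precedes 1 of 2. Eligibility must be confirmed before randomization, which comes before the first dispensing.
- Tracer doses: a test is named at 1 of the 2 tracer visits. For neither dose does the text require the result to be known before injection. In the 5.1.2 procedure list the PET study comes before randomization, and the stated checkpoint is randomization.

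**The case against.** Several points count against a strong reading, and most of them stand in part.

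1. **Section 9.3 does not limit hCG to baseline.** BNP is on the same list (9.3.5), yet BNP at Week 24 is a secondary aim (2.2 f), and 5.1.6 does not name BNP either. Section 8.1 also speaks of laboratory work at designated visits. Table 1 omits even the baseline pregnancy test. So 9.3 and Table 1 are only weak support, and the point rests on what the Week 12 and Week 24 visit texts leave out.
2. **The blood-draw schedule is inconsistent.** Section 9.6 refers to four draws within a year, while the visit text and Table 1 schedule two. A further draw may have been intended, but 9.6 does not say when, and it names no pregnancy test.
3. **Some women may be tested in routine care.** Section 5.1.1 says several PAH drugs require monthly pregnancy monitoring. Bosentan is only the example given. It is excluded here, but other background PAH drugs are allowed (4.4). The share of women covered cannot be found from the documents, and this monitoring is not a trial procedure.
4. **The existing controls are real.** Two contraceptive methods, counselling at Visits 1 and 2, seven calls and the Week 12 criteria review all lower the probability. None of them is a test.
5. **The manual of procedures (8.1) is not available** and may specify tests.
6. **The hazard can be overstated.** The mortality above 50% in 5.1.1 concerns PAH patients who proceed with a pregnancy, not harm from the drug or tracer. Section 9.6 calls the PET radiation small and its risk low, although it does not address pregnancy.

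A reader might infer that re-dispensing and the second tracer would rest on history, contraception and counselling alone, or that no test will be done. The documents do not support either inference, because of points 1, 3 and 5. They support only the statement that the protocol names no test after baseline.

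**Conclusion.** The point holds as a limited statement about the protocol text. A pregnancy test is named only at baseline, although drug is dispensed again 77 to 91 days later and a second radioactive tracer is given 165 to 171 days later. Followed as written, the visit text could leave an early, unrecognised pregnancy undetected before either exposure.

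This rests on three assumptions: the visits fall within their stated windows, the baseline test is done on the day of the baseline visit, and no unseen document adds a test. The number of women of childbearing potential is not stated, so an expected number of events cannot be given; with the controls in place it should be small. The tracer goes to both arms. The re-dispensed capsules are tamoxifen for 12 of the 24 planned subjects and placebo for the other 12.

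This is a cheap improvement in participant safety. No endpoint, power or analysis figure depends on it.

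**What to change.** For women of childbearing potential, in both arms because dispensing is blinded:

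- **5.1.4:** add a urine pregnancy test before the Week 12 dispensing.
- **5.1.6 and 9.3.7:** add a pregnancy test at Week 24 on the urine or blood already collected.
- **5.1.2 and 5.1.6:** require a negative result before tracer injection at both baseline and Week 24.
- State that a positive result holds the drug or the tracer. The withdrawal criteria in 9.4.8 do not name pregnancy and leave it to general safety judgement.
- **Table 1:** add a pregnancy-test row for baseline, Week 12 and Week 24.
- If the manual of procedures already requires these tests, carry them into the protocol.

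With these changes a named test precedes 2 of 2 dispensings and 2 of 2 tracer doses, and the longest interval between named tests falls to at most 94 days (Week 12 to Week 24).

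The cost is one extra urine sample and test at Week 12, one test at Week 24 on a sample already taken, and a short wait before PET. That is 2 added tests per woman concerned. The ceiling is 2 × 24 = 48 if every planned subject were such a woman (more if drop-outs are replaced). The true number will be lower to the extent that men and post-menopausal women are enrolled.

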5.1.7 Telephone follow-up (Week 25)

The research coordinator will call the subject approximately 1 week after the Week 24 visit. Symptoms and potential ongoing side effects after stopping study drug will be assessed. Serious adverse events will continue to be followed until resolution. The research coordinator will once again thank the subject for participation in the study.

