8.1 Personnel training

Prior to randomization of the first subject in the study protocol, the lead investigators will ensure that staff has completed appropriate training and that all documentation including IRB approval is completed and available. The purpose of training is to ensure that study personnel are carrying out the protocol in a consistent way and are adhering to good clinical practice guidelines. Staff will have current Human Subjects Training Certification on file. Before enrollment begins, study coordinators and research assistants who will perform the outcome assessments will be trained in all procedures, including completion of case-report forms (CRFs).

The lead investigators and research staff will constitute the first line of monitoring of the safety of the human participants. Surveillance for AEs will consist of questioning subjects about potential AEs at every study contact, having subjects report any adverse event to the study team, and having subjects undergo vital sign checks and physical exams during each study visit. Laboratories will be performed at designated visits and checked.

All study personnel are required to read the consent form, the protocol and the manual of procedures (MOP).

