9.4 Safety and Adverse events

9.4.1 Definitions of Adverse Events

9.4.1.1 Adverse Event

An adverse event (also known as an adverse experience) is defined as any untoward medical occurrence associated with the use of a drug in humans, whether or not considered drug related. More specifically, an adverse event (can be any unfavorable and unintended sign (e.g., an abnormal laboratory finding), symptom, or disease temporally associated with the use of a drug, without any judgment about causality. An adverse event can arise from any use of the drug (e.g., off-label use, use in combination with another drug) and from any route of administration, formulation, or dose, including an overdose.

Adverse event (AE): Any symptom, sign, illness or experience that develops or worsens in severity during the course of the study. Intercurrent illnesses or injuries should be regarded as AEs. Abnormal results of diagnostic procedures are considered to be AEs if the abnormality:

- results in study withdrawal
- is associated with a serious AE
- is associated with clinical signs or symptoms
- leads to additional treatment or to further diagnostic tests
- is considered by the investigator to be of clinical significance

9.4.1.2 Serious adverse event (SAE): Adverse reactions are classified as serious or non-serious. A **serious adverse event** is any AE that is:

- fatal
- life-threatening
- requires or prolongs hospital stay
- results in persistent or significant disability or incapacity
- a congenital anomaly or birth defect
- an important medical event

Events **not** considered to be serious adverse events are hospitalizations for:

- routine treatment or monitoring of the studied indication, not associated with any deterioration in condition, or for elective procedures
- elective or pre-planned treatment for a pre-existing condition that did not worsen
- emergency outpatient treatment for an event not fulfilling the serious criteria outlined above and not resulting in inpatient admission
- respite care

Important medical events are those that may not be immediately life threatening, but are clearly of major clinical significance. They may jeopardize the subject, and may require intervention to prevent one of the other serious outcomes noted above. For example, drug overdose or abuse, a seizure that did not result in in-subject hospitalization or intensive treatment of bronchospasm in an emergency department would typically be considered serious.

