9.4.6 Interpretation of definitions

AE and UP Reporting Period

The study period during which AEs must be reported is normally defined as the period from the initiation of any study procedures to the end of the study treatment follow-up. For this study, the study treatment follow-up is defined as 14 days following the last administration of study treatment (week 25 phone call follow up).

Preexisting Condition

A preexisting condition is one that is present at the start of the study. A preexisting condition should be recorded as an AE if the frequency, intensity, or the character of the condition worsens during the study period.

General Physical Examination Findings

At screening, any clinically significant abnormality should be recorded as a preexisting condition. At the end of the study, any new clinically significant findings/abnormalities that meet the definition of an AE must also be recorded and documented as an AE.

Post-study AE

All unresolved AEs should be followed by the investigator until the events are resolved, the subject is lost to follow-up, or the AE is otherwise explained. At the last scheduled visit, the investigator should instruct each subject to report any subsequent event(s) that the subject, or the subject's personal physician, believes might reasonably be related to participation in this study. The investigator should notify the study sponsor of any death or AE occurring at any time after a subject has discontinued or terminated study participation that may reasonably be related to this study. The sponsor should also be notified if the investigator should become aware of the development of cancer or of a congenital anomaly in a subsequently conceived offspring of a subject that has participated in this study.

Abnormal Laboratory Values

A clinical laboratory abnormality should be documented as an AE if any one of the following conditions is met:

- The laboratory abnormality is not otherwise refuted by a repeat test to confirm the abnormality
- The abnormality suggests a disease and/or organ toxicity
- The abnormality is of a degree that requires active management; e.g. change of dose, discontinuation of the drug, more frequent follow-up assessments, further diagnostic investigation, etc.

Hospitalization, Prolonged Hospitalization or Surgery

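### For completers, the Week 25 call meant to close the 14-day AE reporting period falls at about day 7, so the second week has no solicited AE contact

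*Combined protocol and SAP*

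**What the plan says.** Two sections of the protocol define the same endpoint of safety follow-up.

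- **9.4.6 (AE and UP Reporting Period):** "the study treatment follow-up is defined as 14 days following the last administration of study treatment (week 25 phone call follow up"). AE reporting runs from the first study procedure to that point.
- **5.1.7:** "The research coordinator will call the subject approximately 1 week after the Week 24 visit". Symptoms and side effects after stopping drug are assessed on this call. No window is given for it.

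The end of dosing for completers is implied by the Week 24 visit list in 5.1.6: "Turn in study diary and any remaining study medication". In Table 1 (5.2), the AE review row has its last entry at Week 25.

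On how AEs are collected, 8.1 describes "questioning subjects about potential AEs at every study contact, having subjects report any adverse event to the study team". By 9.4.1.1 an AE counts "whether or not considered drug related". At the last scheduled visit, 9.4.6 (Post-study AE) has the investigator ask subjects to report later events that they or their personal physician "believes might reasonably be related to participation in this study". Events already known are covered: "All unresolved AEs should be followed by the investigator until the events are resolved" (9.4.6) and "Serious adverse events will continue to be followed until resolution" (5.1.7).

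**The concern.** One call cannot be both about 7 days and 14 days after the last dose. Staff who follow 5.1.7 and Table 1 make the last planned AE inquiry halfway through the period that 9.4.6 says this call closes. In the second half, a new event enters the record only if the subject volunteers it or someone else passes it on. That is weaker ascertainment than in the rest of the trial, where subjects are asked at each contact.

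Safety and side effects are a secondary aim (2.2), and 1.2 stresses safety because the role of estrogen in PAH is unsettled. What is at stake is the completeness of AE capture just after the drug is stopped. The primary endpoint is not touched.

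**Working it through.** **Inputs**

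- Length of the reporting period after the last dose: 14 days (9.4.6).
- Final call: Week 24 visit + about 7 days (5.1.7).
- Last dose: not stated as a calendar day. I take it as the visit day (9.6 holds study medication until after phlebotomy, so a dose that day is possible) or the day before.
- Completers: 12 per arm, 24 in total (7.4).
- Half-lives from 4.1: parent 5 to 7 days; N-desmethyl metabolite about 14 days, with activity described as similar to the parent.

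**Step 1: does the stated 14 days reproduce?** Week 25 − Week 24 = 7 days. It does not. The ±3-day window of the Week 24 visit does not help, because the call is tied to the visit and moves with it.

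**Step 2: days left without a solicited contact**

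| Last dose | Call falls on day | Days uncovered |
|---|---|---|
| Visit day | 7 | 14 − 7 = 7 |
| Day before visit | 8 | 14 − 8 = 6 |
| Supply runs out at dose 168, visit at day 171 | 171 + 7 − 168 = 10 | 14 − 10 = 4 |

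The third row assumes two 12-week kits (3.3). Section 5.1.2 mentions a 13-week supply at baseline, so it may never occur. In none of these cases does the call reach day 14.

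**Step 3: subject-days**

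- Tamoxifen completers: 12 × 7 = 84 of 12 × 14 = 168 (50%), or 12 × 6 = 72 of 168 (43%).
- Both arms: 24 × 7 = 168 of 336, or 24 × 6 = 144 of 336. Half of these belong to placebo subjects, who have no residual drug.

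**Step 4: is drug still present in that week?** Steady state is assumed at Week 24. Parent fraction = 2^(−t/h). Metabolite fraction without further formation = 2^(−t/14). With formation from parent it is exp(−km·t) + km/(kp − km) × (exp(−km·t) − exp(−kp·t)), where k = ln 2 / half-life.

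| Day | Parent (h = 5 to 7) | Metabolite, no formation | Metabolite, with formation |
|---|---|---|---|
| 7 | 38–50% | 71% | 89–91% |
| 14 | 14–25% | 50% | 70–75% |
| 28 | 2–6% | 25% | 38–44% |

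Active drug is present throughout days 8 to 14. The table shows no threshold at day 14, so it does not choose the length of the period.

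**Step 5: scale for a serious event.** Section 4.1 cites 9 thromboembolic events in 455 tamoxifen patients but not the trial's duration. For 12 patients, 12 × 9/455 = 0.237 over that whole trial. Assuming a duration of 12 to 260 weeks, one week carries 0.237/260 = 0.0009 to 0.237/12 = 0.020 events. Section 3.2.2 excludes prior thromboembolism, so the true figure may be lower.

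**The case against.** The best case against is that this is a clerical slip in a parenthesis. A reporting period need not end with a call. Inside the 14 days 9.4.6 still requires reporting, and 8.1 has subjects report any AE. The request limited to related events sits under the post-study heading, so it need not narrow what is reported within the period. Known AEs are followed. Section 9.4.6 also asks for sponsor notification of later deaths or AEs that may be related, and 9.4.7 covers IRB reporting, during or after the study, of events that are unexpected, related and raise risk. Subjects are patients of the same center (3.1.1), and their PAH physician is alerted at completion (5.1.6).

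Most of this stands. The duty to report does not lapse at day 7; only the asking stops. But 8.1 puts questioning at contacts first and sets no time for self-reports. The later safeguards are aimed at known, serious or related events, while the AE definition is wider.

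A text-only correction is also possible. Deleting the parenthesis removes the contradiction but leaves the second week unsolicited. Setting the period to 7 days is consistent, but it halves the period the sponsor chose and ends it with 38–50% of parent and 71–91% of metabolite remaining.

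A reader might infer more than the documents support:

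- **That the half-lives show 14 days to be too short, or require day 28.** No section links residual drug to new AEs after stopping, and the decline singles out neither day.
- **That the missing pregnancy reminder at Weeks 24 and 25 is an error.** No section sets a post-drug contraception period. Contraception is part of routine PAH care (5.1.1), and 9.4.6 asks for notification of a congenital anomaly in later offspring.
- **That serious harm would go unseen or the comparison of arms would be biased.** The schedule is the same in both arms, and the safeguards above would probably bring serious events to light.

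**Conclusion.** The inconsistency is real, and no other section repairs it. For completers, about the second week of the 14-day period has no solicited AE contact: 6 to 7 days per subject, or 72 to 84 subject-days in 12 tamoxifen completers. This rests on a last dose at or about the Week 24 visit and a call close to its nominal day. In the late-visit case where the supply runs out, the gap is 4 days.

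The likely loss is new non-serious events. The one-week thromboembolism figure of at most about 0.02 expected events, under the assumed durations, shows that few serious events are in play. Subjects who stop drug early but keep the schedule may have contacts well past day 14, so the gap mainly concerns completers. No efficacy result or power figure changes. The point is minor and worth correcting because correction costs little.

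**What to change.** Place the final AE call at day 14 after the last dose, window 0 to +3 days (Week 26 for completers), in one of two ways:

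- **Move the Week 25 call.** This adds no call, but the first off-drug contact comes a week later.
- **Keep Week 25 and add one short call at day 14.** This keeps the early check and adds about 24 calls for the existing coordinator.

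In 9.4.6, replace the parenthesis naming the Week 25 call with the new contact, and bring 5.1.7 and Table 1 into line.

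For early stoppers, count actual days since the last dose. Any contact already scheduled at or after day 14 serves. An exemption by nominal week should not be used. For example, a stop at Week 23 (day 161) is nominally 14 days before the Week 25 call (day 175). If the Week 24 visit is 3 days early (day 165), the call falls on day 172, only 11 days after the last dose.

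Either way, follow-up runs about 1 week longer, and masking with it, since 4.5 keeps it until the last subject finishes. No new visit, test, staff member or patient is needed. A day-28 call, a pregnancy reminder at Week 24 and the final call, and a separate table of AEs starting after the last dose are options for the sponsor and not part of the correction.
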